The ability to use the pediatric formulation (RTS,S/AS01_E) for adults would be a very positive step when considering product availability and implementation feasibility of a mass vaccination program in the context of an elimination campaign, therefore study aims c) and d) are being investigated. The pediatric formulation of RTS,S/AS01 has never been used in adults, but there are indications from other programs that the AS01_E Adjuvant System may not be substantially inferior to AS01_B for immunogenicity [EARLY-CLINRES-002, data on file; Montoya, 2013].

Evaluation of a two-dose schedule, separated by seven months, will contribute to explore the possibility that the close repetition of doses leads to some excessive priming that may be detrimental to the immune responses. If leading to sufficient protection, a two-dose strategy may be a great advantage when considering cost and logistics aspects in the contribution to malaria control and elimination efforts.

Rationale for the study design

This study is designed to evaluate efficacy, immunogenicity and safety of various dose schedules of GSK Biologicals' candidate malaria vaccines RTS,S/AS01_B (adult formulation containing 50 µg RTS,S antigen and AS01_B formulation with 50 µg of MPL and 50 µg of QS-21 per 0.5 ml) and RTS,S/AS01_E (pediatric formulation containing 25 µg RTS,S antigen and AS01_E formulation with 25 µg of MPL and 25 µg of QS-21 per 0.5 ml) in healthy malaria-naïve subjects aged 18-55 years. The study proposed herein will include six study groups. Four of these study groups will be vaccinated according to a 0, 1, 7-month schedule and one according to a 0, 7-month schedule. The immunization schedule of reference will be the same as the one used in study MALARIA-071 (117014), i.e. RTS,S/AS01_B full dose at Month 0 and Month 1 and RTS,S/AS01_B 1/5th dose at Month 7. Three months after the last dose of study vaccines, all subjects will undergo a sporozoite challenge and will be compared to an infectivity control group:

- **Group AduFx** will receive RTS,S/AS01_B full dose at Month 0 and Month 1 + RTS,S/AS01_B fractional dose (1/5th dose) at Month 7 (immunization schedule of reference).
- **Group 2PedFx** will receive double dose of RTS,S/AS01_E at Month 0 and Month 1 + double dose of RTS,S/AS01_E fractional dose (1/5th dose) at Month 7.
- **Group PedFx** will receive RTS,S/AS01_E full dose at Month 0 and Month 1 + RTS,S/AS01_E fractional dose (1/5th dose) at Month 7.

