- **Group Adu2Fx** will receive RTS,S/AS01_B full dose at Month 0 + RTS,S/AS01_B fractional dose (1/5th dose) at Month 1 and Month 7.
- **Group Adu1Fx** will receive RTS,S/AS01_B full dose at Month 0 + RTS,S/AS01_B fractional dose (1/5th dose) at Month 7.
- **Group infectivity control** will not receive any immunization but will undergo the sporozoite challenge.

The sporozoite challenge model, in the RTS,S/AS candidate vaccine development program, has demonstrated a high relevance in its ability to predict efficacy under conditions of natural exposure in malaria-endemic countries. The study design is similar to that of other past CHMI studies successfully conducted. To better discriminate levels of protection across study groups and assess durability of protection, CHMI will occur three months after the last vaccine dose rather than three weeks as in past RTS,S studies. About 150 healthy adults will be enrolled and followed up closely under controlled conditions by investigators experienced in *P. falciparum* challenge studies. The proportion of immunized participants who remain free of *P. falciparum* infection following sporozoite challenge and the delay in the pre-patent period leading to infection will be evaluated as indicators of vaccine-induced protection. Immunological investigations are planned with the intent to characterize qualitatively and quantitatively the immune response induced by the immunization regimen. This design takes into account logistical restrictions on the size of human challenge procedures.

Immunological assays will be selected for their ability to demonstrate whether the administration of a fractional vaccine dose can affect quantitatively or qualitatively the vaccine-induced immune response, especially when considering the generation of antibodies against the circumsporozoite protein of *P. falciparum* (CS) antigen, but also the hepatitis B surface antigen (HBsAg) which is present in the vaccine construct. Qualitative aspect of the immune response will be characterized as much as possible (targeting different parts of the antigen and avidity). Samples from this study may be used in future assay development or testing to better understand the immune responses underlying vaccine induced protection, responses to the vaccine components and the disease under investigation.

Objectives**Primary***Efficacy*

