 - Anti-HBs IgG antibody concentrations before vaccine administration (Day 0), one month post-Dose 2 (Day 58), six months post-Dose 2 (Day 196), one month post-Dose 3 (Day 226), on the day of challenge (Day 286), 28 days post-challenge (Day 314), and at study end (Day 376) for subjects from AduFx, 2PedFx, PedFx, and Adu2Fx groups and before vaccine administration (Day 0), before Dose 2 (Day 196), one month post-Dose 2 (Day 226), on the day of challenge (Day 286), 28 days post-challenge (Day 314), and at study end (Day 376) for subjects from Adu1Fx group.

Safety

- Safety and reactogenicity of the investigational vaccine for each vaccination schedule:
 - Occurrence of solicited local and general AEs within seven days (day of vaccination and six subsequent days) after each vaccination.
 - Occurrence of unsolicited AEs within 30 days (day of vaccination and 29 subsequent days) after each vaccination, according to the Medical Dictionary for Regulatory Activities (MedDRA) classification.
 - Occurrence of AEs within 30 days (day of challenge and 29 subsequent days) after challenge, according to the MedDRA classification.
 - Occurrence of SAEs (all, fatal, related to investigational vaccine) within 30 days (day of vaccination and 29 subsequent days) after each vaccination, according to the MedDRA classification.
 - Occurrence of SAEs (all, fatal, related to investigational vaccine) during the whole study period (from Dose 1 [Day 0] up to study conclusion [Day 376]), according to the MedDRA classification.

- Occurrence of AEs and SAEs leading to withdrawal from further vaccination from Dose 1 (Day 0) up to study conclusion (Day 376), according to the MedDRA classification, for each vaccinated subject.
- Occurrence of pIMDs from Dose 1 (Day 0) up to study conclusion (Day 376), according to the MedDRA classification, for each vaccinated subject.
- Occurrence of meningitis from Dose 1 (Day 0) up to study conclusion (Day 376), according to the MedDRA classification, for each vaccinated subject.
- Occurrence of abnormal laboratory values at screening, Day 35, Day 58, Day 203, Day 226, the day of first parasitemia, and Day 314 for each vaccinated subject and at screening, the day of first parasitemia and Day 314 for the infectivity control subjects.
- Safety after sporozoite challenge in the infectivity control group.
 - Occurrence of AEs within 30 days (day of challenge and 29 subsequent days) after challenge, according to the MedDRA classification.

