1.2.2. Rationale for the study design

This study is designed to evaluate efficacy, immunogenicity and safety of various dose schedules of GSK Biologicals' candidate malaria vaccines RTS,S/AS01_B (adult formulation containing 50 µg RTS,S antigen and AS01_B formulation with 50 µg of MPL and 50 µg of QS-21 per 0.5 ml) and RTS,S/AS01_E (pediatric formulation containing 25 µg RTS,S antigen and AS01_E formulation with 25 µg of MPL and 25 µg of QS-21 per 0.5 ml) in healthy malaria-naïve subjects aged 18-55 years. The study proposed herein will include six study groups. Four of these study groups will be vaccinated according to a 0, 1, 7-month schedule and one according to a 0, 7-month schedule. The immunization schedule of reference will be the same as the one used in study MALARIA-071 (117014), i.e. RTS,S/AS01_B full dose at Month 0 and Month 1 and RTS,S/AS01_B 1/5th dose at Month 7. Three months after the last dose of study vaccines, all subjects will undergo a sporozoite challenge and will be compared to an infectivity control group:

- **Group AduFx** will receive RTS,S/AS01_B full dose at Month 0 and Month 1 + RTS,S/AS01_B fractional dose (1/5th dose) at Month 7 (immunization schedule of reference).
- **Group 2PedFx** will receive double dose of RTS,S/AS01_E at Month 0 and Month 1 + double dose of RTS,S/AS01_E fractional dose (1/5th dose) at Month 7.
- **Group PedFx** will receive RTS,S/AS01_E full dose at Month 0 and Month 1 + RTS,S/AS01_E fractional dose (1/5th dose) at Month 7.
- **Group Adu2Fx** will receive RTS,S/AS01_B full dose at Month 0 + RTS,S/AS01_B fractional dose (1/5th dose) at Month 1 and Month 7.
- **Group Adu1Fx** will receive RTS,S/AS01_B full dose at Month 0 + RTS,S/AS01_B fractional dose (1/5th dose) at Month 7.
- **Group infectivity control** will not receive any immunization but will undergo the sporozoite challenge.

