11.11. Interpretation of analyses

For the primary efficacy evaluations the aim will be to establish significant vaccine efficacy over infectivity controls whereas secondary efficacy evaluations between vaccination schedules will be descriptive with the aim to characterize the difference in immunogenicity, efficacy and safety between groups.

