Visit 1b (Screening) → Visit 11 (Challenge)	0 to 56 days	-
Visit 11 → Visit 30	28 days	± 7 days

¹ Whenever possible the investigator should arrange study visits within this interval.

² Subjects may not be eligible for inclusion in the ATP cohort for analysis of immunogenicity and efficacy if they make the study visit outside this interval.

The following group names will be used for the statistical analyses:

Group order in tables	Group label in tables	Group definition for footnote
1	AduFx	RTS,S/AS01 _B full dose administered at Month 0, Month 1 and RTS,S/AS01 _B 1/5 th dose administered at Month 7
2	2PedFx	RTS,S/AS01 _E double dose administered at Month 0, Month 1 and double dose RTS,S/AS01 _E 1/5 th dose administered at Month 7
3	PedFx	RTS,S/AS01 _E full dose administered at Month 0, Month 1 and RTS,S/AS01 _E 1/5 th dose administered at Month 7
4	Adu2Fx	RTS,S/AS01 _B full dose at Month 0 and RTS,S/AS01 _B 1/5 th dose administered at Month 1, Month 7
4	Adu1Fx	RTS,S/AS01 _B full dose at Month 0 and RTS,S/AS01 _B 1/5 th dose administered at Month 7
5	Control	Subjects will not receive any immunization but will undergo sporozoite challenge

Two defined pooled groups:

Group order in tables	Group label in tables	Group definition for footnote
1	P	All subjects who have not been infected by P. falciparum parasitemia (defined by a positive blood slide) during the challenge and were part of one of the vaccinated groups
2	NP	All subjects who have been infected by P. falciparum parasitemia (defined by a positive blood slide) during the challenge and were part of one of the vaccinated groups

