6.5. Analysis of safety

6.5.1. Analysis of safety planned in the protocol

The analysis of safety will be performed on the ITTS.

The percentage of subjects with at least one local AE (solicited and unsolicited), with at least one general AE (solicited and unsolicited) and with any AE during the 7-day or 30-day follow-up period after each vaccine dose and overall will be tabulated with exact 95% CI. The percentage of doses followed by at least one local AE (solicited and unsolicited), by at least one general AE (solicited and unsolicited) and by any AE during the 7-day or 30-day follow-up period will be tabulated with exact 95% CI. The same computations will be done for Grade 3 AEs, for any AEs considered related to vaccination and for any Grade 3 AEs considered related to vaccination.

The percentage of subjects reporting each individual solicited local AE (any grade and Grade 3) and each individual solicited general AE (any grade, Grade 3, any related, Grade 3 related, resulting in medically attended visit) during the 7-day follow-up period (Day 0-6) after each vaccine dose and overall will be tabulated for each group. Similarly, the percentage of doses followed by each individual solicited local and general AE will be tabulated, for the overall and for each vaccination course, with exact 95% CI.

For fever (fever is defined as temperature $\geq 37.5^{\circ}\text{C}/99.5^{\circ}\text{F}$ for oral, axillary or tympanic route, or $\geq 38.0^{\circ}\text{C}/100.4^{\circ}\text{F}$ for rectal route), the number and percentage of subjects reporting fever by half degree ($^{\circ}\text{C}$) cumulative increments during the first seven days (Day 0-6) after each vaccine dose and overall will be tabulated. Similar tabulations will be performed for any fever with a causal relationship to vaccination and Grade 3 ($> 39.0^{\circ}\text{C}$) causally related fever. The maximum temperature reported over the 7-day follow-up period (Day 0-6) overall doses will be tabulated.

The percentage of subjects reporting unsolicited AEs within 30 days (Day 0-29) after each vaccine dose (overall doses) and percentage of subjects reporting AEs after the sporozoite challenge will be tabulated by group and by MedDRA preferred term with exact 95% CI. Similar tabulation will be done for Grade 3 unsolicited AEs, for any causally related unsolicited AEs and for Grade 3 causally related unsolicited AEs.

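### Three schedules give the same RTS,S/AS01B first dose, yet Dose 1 reactogenicity is tabulated only by schedule (planned N=26 each), with no pooled AS01B estimate (planned N=78)

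*Protocol*

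**What the plan says.** Protocol section 1.2.2 sets out the three AS01B schedules. AduFx "will receive RTS,S/AS01_B full dose at Month 0 and Month 1 + RTS,S/AS01_B fractional dose (1/5th dose) at Month 7". Adu2Fx "will receive RTS,S/AS01_B full dose at Month 0 + RTS,S/AS01_B fractional dose (1/5th dose) at Month 1 and Month 7". Adu1Fx "will receive RTS,S/AS01_B full dose at Month 0 + RTS,S/AS01_B fractional dose (1/5th dose) at Month 7". Tables 3 and 21 of the protocol show the same Day 0 product and volume (0.5 ml) for all three, and Table 21 the same route, site and side. The schedules separate only at Visit 3.

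PedFx and 2PedFx receive RTS,S/AS01E on Day 0, at 0.5 ml and 1.0 ml. Protocol section 1.2.1 states: "The pediatric formulation of RTS,S/AS01 has never been used in adults". Use of this formulation in adults, at single and at double volume, makes up study aims c and d.

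The safety endpoint (Synopsis; Protocol 11.2.3; SAP 4.2.3) is "Occurrence of solicited local and general AEs within seven days (day of vaccination and six subsequent days) after each vaccination", for each vaccination schedule. SAP 6.5.1 says that the percentages for each solicited event "after each vaccine dose and overall will be tabulated for each group". In that sentence the overall figure runs across doses, not across groups. Templates 20 to 22 of the SAP have one column per group. SAP section 2 introduces "Two defined pooled groups", and both are defined by protection status after challenge. Neither combines groups by the product given at Dose 1.

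Protocol 11.11 describes the evaluations between schedules as descriptive, "with the aim to characterize the difference in immunogenicity, efficacy and safety between groups".

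**The concern.** Until Dose 2, the three AS01B groups are one randomised arm for reactogenicity. Dose 1 is also the cleanest point at which to compare the two formulations, because no earlier dose and no drop-out between doses has intervened. The plan gives three separate estimates of what should be one rate, each from at most 26 subjects, and never the combined one. A reader of the Visit 2 rows who wants to know how the pediatric formulation compares with the adult one has three wide AS01B intervals to choose from. Characterising safety differences between groups is a stated aim, so the precision of that description matters even though no test is planned.

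**Working it through.** **Plan's own figure.** Protocol 11.4 gives power for efficacy only. Neither document states a precision or power figure for reactogenicity, so there is none to reproduce.

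**Inputs.**
- 26 subjects per vaccine group (Protocol 5.1), all five vaccine groups randomised together (Protocol 6.2.2.2.1).
- Identical Day 0 injection in AduFx, Adu2Fx and Adu1Fx (Protocol Tables 3 and 21), so 3 x 26 = 78 planned AS01B recipients at Dose 1.
- Exact Clopper-Pearson intervals within group (SAP 11.1).
- Event rates are not in the documents. About 19% and about 20% are assumed for illustration, and the zero-event case needs no rate.

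**AS01B estimate alone.**
- 5/26 = 19.2%: exact 95% CI 6.6% to 39.4%, a width of 32.8 points.
- 15/78 = 19.2%: exact 95% CI 11.2% to 29.7%, a width of 18.5 points.
- Zero events, upper limit 1 - 0.025^(1/n): 13.2% for n = 26 and 4.6% for n = 78.

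**Contrast with one pediatric-formulation group of 26.** PedFx and 2PedFx have different first doses, so that side stays at 26. For a common rate the standard error is proportional to the square root of (1/n1 + 1/n2):
- Ratio = sqrt(1/26 + 1/78) / sqrt(1/26 + 1/26) = sqrt(4/78) / sqrt(6/78) = sqrt(2/3) = 0.816, a reduction of 18%.
- At 20% in both groups the normal-approximation 95% half-width is 1.96 x sqrt(0.16 x 2/26) = 21.7 points, against 1.96 x sqrt(0.16 x (1/26 + 1/78)) = 17.8 points.
- At other assumed common rates: 16.3 against 13.3 points at 10%, 24.9 against 20.3 at 30%, and 27.2 against 22.2 at 50%.

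**Spread among identical groups.** If the true rate were 20% in all three AS01B groups of 26, binomial variation alone would separate the highest from the lowest by at least 4/26 (15.4 points) with probability 44%, by full enumeration. Apparent Dose 1 differences between these schedules should therefore be common even when nothing differs.

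**How far pooling reaches.** The Day 0-6 solicited window closes well before any second dose. The 30-day unsolicited window does not. Protocol Table 9 allows Visit 3 at 28 ± 7 days, so Dose 2 may be given from Day 21 in AduFx and Adu2Fx, while Adu1Fx has no Month 1 dose. Pooling unsolicited events over a fixed period is clean only for Day 0 to Day 20.

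**The case against.** The strongest reply is that no planned comparison is weakened. The documents name no safety comparator and plan no safety test or difference. SAP section 7 makes every analysis descriptive, and AduFx is the reference for efficacy and the antibody comparison tables. All 78 recipients appear side by side, and a reader can add three counts. This stands as to the kind of loss. A reader might infer that two thirds of the comparator is thrown away, and the documents do not support that. What is missing is a pooled estimate with its interval, and a difference with its interval. Precision is what a descriptive analysis has to offer, so the reply limits the point without removing it.

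A reader might also infer that the plan loses a quantifiable amount of power. It does not. There is no reactogenicity test, any rates would be assumed, and the gain would depend on which formulation has the higher rate.

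Nor can it be said that Dose 1 differences among the three AS01B groups can only be chance. The study is open label and solicited symptoms are self-reported on diary cards, so knowledge of the schedule could affect reporting. That is a reason to keep the by-schedule columns beside the pooled one.

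Finally, the protocol's background section reports high general reactogenicity after a second immunization in an earlier study. Pooling does nothing for Dose 2, where the AS01B groups no longer receive the same treatment. That is correct, and it bounds the benefit.

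**Conclusion.** The point holds as a modest, inexpensive improvement in precision. It is not an error in a planned comparison and does not touch the primary objective. Pooling the identical Dose 1 recipients would cut the zero-event upper limit for AS01B from 13.2% to 4.6%, narrow its interval at about 19% incidence from 32.8 to 18.5 points, and reduce the standard error of a contrast with PedFx or 2PedFx by 18%.

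These figures assume the planned 26 per group. Solicited-symptom denominators count only doses with a completed symptom sheet (SAP 11.2.5), so the actual numbers may be smaller. The incidence values are illustrative. The conclusion is confined to Dose 1, and is straightforward only for solicited events.

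**What to change.** In the SAP, define a third pooled group for Dose 1 only: RTS,S/AS01B full dose, Dose 1 (AduFx + Adu2Fx + Adu1Fx), planned N=78. Show it in the Visit 2 rows of Templates 21 and 22 and of the Day 0-6 version of Template 20, beside the existing by-schedule columns. Report the PedFx and 2PedFx differences from it with a 95% confidence interval, labelled descriptive. Name the interval method, because SAP 11.1 covers only a proportion within one group. A separate small Dose 1 table avoids a column left empty at later visits and in the overall rows.

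If unsolicited events are pooled too, give them their own Dose 1 table restricted to Day 0-20. The planned Template 23 summaries cover 30 days after any vaccination and have no Dose 1 rows, and a window to Day 27 could take in events after Dose 2.

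The cost is one small extra table (two if unsolicited events are included) and a sentence on the interval method. No new data are needed, and enrolment, dosing and conduct do not change.

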Figure 1 Study design	47

LIST OF APPENDICES

	PAGE
APPENDIX A LABORATORY ASSAYS	130
APPENDIX B CLINICAL LABORATORIES	132
APPENDIX C NHANES I CARDIOVASCULAR RISK CRITERIA.....	133
APPENDIX D AMENDMENTS AND ADMINISTRATIVE CHANGES TO THE PROTOCOL.....	136

LIST OF ABBREVIATIONS

012M:	Group of subjects enrolled in study MALARIA-071, who were randomized to receive three full doses of RTS,S/AS01 _B at Month 0, Month 1 and Month 2.
AduFx:	Subjects receiving RTS,S/AS01 _B full dose at Month 0, Month 1 + RTS,S/AS01 _B 1/5 th dose at Month 7
Adu1Fx:	Subjects receiving RTS,S/AS01 _B full dose at Month 0 + RTS,S/AS01 _B 1/5 th dose at Month 7
Adu2Fx:	Subjects receiving RTS,S/AS01 _B full dose at Month 0 + RTS,S/AS01 _B 1/5 th dose at Month 1, Month 7
AE:	Adverse event
ALT:	Alanine aminotransferase
Anti-CS:	Antibody to the Plasmodium falciparum circumsporozoite (CS) repeat domain
Anti-HBs:	Antibody to the hepatitis B surface antigen
AS01_B:	GSK's proprietary Adjuvant System containing MPL, QS-21 and liposome (50 µg MPL and 50 µg QS-21)
AS01_E:	GSK's proprietary Adjuvant System containing MPL, QS-21 and liposome (25 µg MPL and 25 µg QS-21)
AST:	Aspartate aminotransferase
ATP:	According-to-protocol
β-HCG:	Beta-human chorionic gonadotropin
CEVAC:	Center for vaccinology, Ghent University, Belgium
CHMI:	Controlled human malaria infection
CI:	Confidence interval
CLIA:	Chemiluminescence enzyme immunoassay
CLS:	Clinical laboratory sciences
CS:	Circumsporozoite protein of Plasmodium falciparum
C-term:	CS terminal portion of the protein

DoC:	Day of challenge
eCRF:	Electronic case report form
EDD:	Estimated date of delivery
EGA:	Estimated gestational age
ELISA:	Enzyme-linked immunosorbent assay
EPT:	Endpoint titer
eTDF:	Electronic temperature excursion decision form
FDA:	Food and Drug Administration, United States of America
Fx:	Fractional
Fx017M:	Group of subjects enrolled in study MALARIA-071, who were randomized to receive two full doses of RTS,S/AS01 _B at Month 0 and Month 1 and a third fractional dose (1/5 th dose) at Month 7.
GCP:	Good clinical practice
GMC:	Geometric mean concentration
GSK:	GlaxoSmithKline
HBsAg:	Hepatitis B surface antigen
HCV:	Hepatitis C virus
HIV:	Human immunodeficiency virus
IB:	Investigator brochure
ICF:	Informed consent form
ICH:	International conference on harmonization
IEC:	Independent ethics committee
IgG:	Immunoglobulin G
IM:	Intramuscular
IMP:	Investigational medicinal product
IND:	Investigational new drug

IRB:	Institutional review board
LMP:	Last menstrual period
MedDRA:	Medical dictionary for regulatory activities
MPL:	3-O-desacyl-4'-monophosphoryl lipid A (produced by GSK)
mRNA:	messenger ribonucleic acid
NHANES I:	National health and nutrition examination survey I
PBMC:	Peripheral blood mononuclear cells
PCR:	Polymerase chain reaction
PedFx:	Subjects receiving RTS,S/AS01 _E full dose at Month 0, Month 1 + RTS,S/AS01 _E 1/5 th dose at Month 7
2PedFx:	Subjects receiving RTS,S/AS01 _E double dose at Month 0, Month 1 + double dose RTS,S/AS01 _E 1/5 th dose at Month 7
P. falciparum:	Plasmodium falciparum
pIMD:	Potential immune-mediated disease
QS-21:	(Quillaja saponaria Molina, fraction 21) (Licensed by GSK from Antigenics Inc, a wholly owned subsidiary of Agenus Inc., a Delaware, USA corporation)
RTS,S:	Particulate antigen, containing both RTS and S (hepatitis B surface antigen) proteins
RTS,S/AS01_B:	GSK Biologicals' candidate Plasmodium falciparum malaria vaccine adjuvanted with GSK Biologicals' proprietary Adjuvant System AS01 _B
RTS,S/AS01_E:	GSK Biologicals' candidate Plasmodium falciparum malaria vaccine adjuvanted with GSK Biologicals' proprietary Adjuvant System AS01 _E
SAE:	Serious adverse event
SBIR:	Randomization system on internet
SD:	Standard deviation

SDV:	Source document verification
SOP:	Standard operating procedure
SPM:	Study procedures manual
TVC:	Total vaccinated cohort
ULN:	Upper limit of normal range
WBC:	White blood cells
WHB:	Whole blood
WRAIR:	Walter Reed Army Institute of Research

GLOSSARY OF TERMS

- Adequate contraception:** Adequate contraception is defined as a contraceptive method with failure rate of less than 1% per year when used consistently and correctly and when applicable, in accordance with the product label for example:
- abstinence from penile-vaginal intercourse, when this is their preferred and usual lifestyle,
 - Oral contraceptives , either combined or progestogen alone,
 - injectable progestogen,
 - implants of etenogestrel or levonorgestrel,
 - estrogenic vaginal ring,
 - percutaneous contraceptive patches,
 - intrauterine device or intrauterine system,
 - male partner sterilization prior to the female subject's entry into the study, and this male is the sole partner for that subject,

The information on the male sterility can come from the site personnel's review of the subject's medical records; or interview with the subject on her medical history.

- male condom combined with a vaginal spermicide (foam, gel, film, cream or suppository)
- male condom combined with a female diaphragm, either with or without a vaginal spermicide (foam, gel, film, cream, or suppository).

Adequate contraception does not apply to subjects of child bearing potential with same sex partners, when this is their preferred and usual lifestyle.

- Adverse event:** Any untoward medical occurrence in a patient or clinical investigation subject, temporally associated with the use of a medicinal product, whether or not considered related to the medicinal product.

An adverse event (AE) can therefore be any unfavorable and unintended sign (including an abnormal laboratory finding), symptom, or disease (new or exacerbated) temporally associated with the use of a medicinal product. For marketed medicinal products, this also includes failure to produce expected benefits (i.e. lack of efficacy), abuse or misuse.

Blinding:	A procedure in which one or more parties to the trial are kept unaware of the treatment assignment in order to reduce the risk of biased study outcomes. The level of blinding is maintained throughout the conduct of the trial, and only when the data are cleaned to an acceptable level of quality will appropriate personnel be unblinded or when required in case of a serious adverse event. In an open-label study, no blind is used. Both the investigator and the subject know the identity of the treatment assigned.
Eligible:	Qualified for enrolment into the study based upon strict adherence to inclusion/exclusion criteria.
Electronic case report form:	Auditable electronic record designed to capture information required by the clinical trial protocol to be reported to the sponsor on each trial subject.
Epoch:	An epoch is a self-contained set of consecutive timepoints or a single timepoint from a single protocol. Self-contained means that data collected for all subjects at all timepoints within that epoch allows to draw a complete conclusion to define or precise the targeted label of the product (e.g. primary, booster, yearly immunogenicity follow-ups, and surveillance periods for efficacy or safety).
eTrack:	GSK's tracking tool for clinical trials.
Evaluable:	Meeting all eligibility criteria, complying with the procedures defined in the protocol, and, therefore, included in the according-to-protocol (ATP) analysis.
Immunological correlate of protection:	The defined immune response above which there is a high likelihood of protection in the absence of any host factors that might increase susceptibility to the infectious agent.
Investigational vaccine: (Synonym of Investigational Medicinal Product)	A pharmaceutical form of an active ingredient or placebo being tested or used as a reference in a clinical trial, including a product with a marketing authorization when used in a way different from the approved form, or when used for an unapproved indication, or when used to gain further information about an approved use.
Menarche:	Menarche is the onset of menses for the first time in a young female and is preceded by several changes associated with puberty including breast development and pubic hair growth. Menarche usually occurs within 1-2 years of breast development, thelarche. However, a young

female can become pregnant before her first menses. Thus, a conservative definition of non-childbearing potential in a pre-menarcheal female is a young female who has not yet entered puberty as evidenced by lack of breast development (palpable glandular breast tissue).

Menopause:	Menopause is the age associated with complete cessation of menstrual cycles, menses, and implies the loss of reproductive potential by ovarian failure. A practical definition accepts menopause after 1 year without menses with an appropriate clinical profile at the appropriate age e.g. > 45 years.
Potential Immune-Mediated Disease:	Potential immune-mediated diseases (pIMDs) are a subset of AEs that include autoimmune diseases and other inflammatory and/or neurologic disorders of interest which may or may not have an autoimmune etiology.
Primary completion date:	The date that the final subject was examined or received an intervention for the purpose of final collection of data for the primary outcome, whether the clinical trial concluded according to the pre-specified protocol or was terminated.
Protocol amendment:	The International Conference on Harmonization (ICH) defines a protocol amendment as: ‘A written description of a change(s) to or formal clarification of a protocol.’ GSK Biologicals further details this to include a change to an approved protocol that affects the safety of subjects, scope of the investigation, study design, or scientific integrity of the study.
Protocol administrative change:	A protocol administrative change addresses changes to only logistical or administrative aspects of the study.
Randomization:	Process of random attribution of treatment to subjects in order to reduce bias of selection.
Self-contained study:	Study with objectives not linked to the data of another study.
Serious adverse event:	A serious adverse event (SAE) is any untoward medical occurrence that: 
 • results in death; • is life-threatening; • requires hospitalization or prolongation of existing hospitalization; • results in disability/incapacity;

Medical or scientific judgment should be exercised in deciding whether reporting is appropriate in other situations, such as important medical events that may not be immediately life-threatening or result in death or hospitalization but may jeopardize the subject or may require medical or surgical intervention to prevent one of the other outcomes listed in the above definition. These should also be considered serious. Examples of such events are invasive or malignant cancers, intensive treatment in an emergency room or at home for allergic bronchospasm or blood dyscrasias or convulsions that do not result in hospitalization.

In this study, the following AEs of specific interest: pIMDs and meningitis will be reported as SAEs.

- Site Monitor:** An individual assigned by the sponsor who is responsible for assuring proper conduct of clinical studies at one or more investigational sites.
- Solicited adverse event:** Adverse events to be recorded as endpoints in the clinical study. The presence/occurrence/intensity of these events is actively solicited from the subject or an observer during a specified post-vaccination follow-up period.
- Subject:** Term used throughout the protocol to denote an individual who has been contacted in order to participate or participates in the clinical study, either as a recipient of the vaccine(s)/product(s) or as a control.
- Subject number:** A unique number identifying a subject, assigned to each subject consenting to participate in the study.
- Treatment:** Term used throughout the clinical study to denote a set of investigational product(s) or marketed product(s) or placebo intended to be administered to a subject, identified by a unique number, according to the study randomization or treatment allocation.
- Treatment number:** A number identifying a treatment to a subject, according to the study randomization or treatment allocation.
- Unsolicited adverse event:** Any AE reported in addition to those solicited during the clinical study. Also any 'solicited' symptom with onset outside the specified period of follow-up for solicited symptoms will be reported as an unsolicited adverse event.

TRADEMARKS

The following trademarks are used in the present protocol.

Note: In the body of the protocol (including the synopsis), the names of the products will be written without the superscript symbol TM or ® and in *italics*.

Trademarks of the GlaxoSmithKline group of companies	Generic description
Malarone®	Atovaquone and proguanil hydrochloride

Trademarks not owned by the GlaxoSmithKline group of companies	Generic description
QS-21 (Quillaja saponaria Molina, fraction 21; licensed by GSK from Antigenics Inc, a wholly owned subsidiary of Agenus Inc., a Delaware, USA corporation)	Triterpene glycoside immune enhancer
Imodium® (Johnson & Johnson Limited)	Loperamide
Coartem® (Novartis Pharmaceuticals UK Ltd.)	Artemether/lumefantrine

